## Protocol Populations

### Protocol Version 4 Population (PV4ANY)

The "Protocol Version 4" population is any patient who consented to Protocol version 4 (or higher) at any point in the study. The protocol version is taken from the Protocol CRF page.

### Last Protocol Consented to: 1 or 2 (PV1N2)

The "Last Protocol Consented to: 1 or 2" population includes any patient who consented to Protocol version 1 or 2 as their most recent version. The protocol version is taken from the Protocol CRF page.

### Last Protocol Consented to: 3 or higher (PV3PLUS)

The "Last Protocol Consented to: 3 or higher" population includes any patient who consented to Protocol version 3 or higher as their most recent version. The protocol version is taken from the Protocol CRF page.

### **Last Protocol Consented to: 5 or higher (PV5PLUS)**

The "Last Protocol Consented to: 5 or higher" population includes any patient who consented to Protocol version 5 or higher as their most recent version. The protocol version is taken from the Protocol CRF page.

### **Protocol Version 3 (+) 12 Month Follow-up Completion (PV3COMP)**

The "Protocol Version 3 (+) 12 Month Follow-up Completion" population includes any patient who consented to Protocol version 3 or higher at any time (according to the Protocol CRF page) and completed the study according to their 12 month FU record from the DS CRF.

## **Efficacy Populations**

Outputs will be repeated by given populations combinations as defined in the LoPO and in this document.

### **Intent-to-Treat Population (IT)**

The "Intent-to-Treat" population is any patient who took at least one dose of study medication according to the dose accountability CRF page. A patient was considered dosed if they had a 'number of capsules taken' record according to the exposure CRF page that wasn't zero or missing.

### **mBCC Protocol 4 (+) Population (MBCC)**

The "mBCC Protocol 4 (+)" population was any patient who had all of the following criteria:

- Consented to Protocol version 4 or Higher as a first version according to the CRF.
- Had a metastatic disease status according to the CRF.

### **8 Weekly Tumour Assessment Population (TU8)**

The "8 Weekly Tumour Assessment" population was any patient who had all of the following criteria:

- Tumour assessments every 8 weeks (+/- 10 days of the expected date of the next assessment) since consenting Protocol version 4. Protocol signing date taken from CRF page defining consent. Tumour assessment visits taken from the CRF page defining tumour information.
- Did not miss ANY tumour assessments since consenting to Protocol version 4.

The population also includes all patients from the MBCC population, regardless of whether they meet the aforementioned criteria.

### **Symptomatic Patients (SYMP)**

Clinical Science manually reviewed all Metastatic patients to determine which subjects had symptoms of the disease. This was completed by looking at numerous data including medical history information. The “Symptomatic Patients” population were the patients who were considered symptomatic by Clinical Science Review.

### **Non-Symptomatic Patients (NSYMP)**

Clinical Science manually reviewed all Metastatic patients to determine which subjects had symptoms of the disease. This was completed by looking at numerous data including medical history information. The “Non-Symptomatic Patients” population were the patients who were considered non-symptomatic by Clinical Science Review.

### **Measurable Disease Patients**

Some outputs require the subset of Measurable Disease Patients only. This subset would consist of patients with a target measurable disease at Baseline. This is identified within the titles and footnotes of the relevant outputs.

### **Histologically Confirmed Disease Patients**

Some outputs require the subset of Histologically Confirmed Disease Patients only. This subset would consist of patients with histologically confirmed disease as per PDMS. This is identified within the titles and footnotes of the relevant outputs.

### **Measurable and Histologically Confirmed Disease Patients**

Some outputs require the subset of Measurable and Histologically Confirmed Disease Patients. This subset would consist of patients with a target measurable disease at Baseline as well as histologically confirmed disease as per PDMS. This is identified within the titles and footnotes of the relevant outputs.

## Other Populations

### Potentially Reversible AE Population (PV3DSC6M)

The "Potentially Reversible AE" population is defined as the patients who consented to protocol version 3 or higher at any point during the study (from the CRF), excluding:

- Patients who discontinued treatment within 6 months of the cut (discontinue date from the CRF).
- Patients who were lost to follow-up within 6 months of treatment discontinuation (both from CRF).
- Patients who died within 6 months of treatment discontinuation (both from CRF).

The reason for inclusion of only patients who consented to version 3 or higher is due to the fact that patients consenting to earlier versions were only subject to a 1 month follow up period.

## Output Specifications: Demography Outputs

### Patient Populations:

	Locally Advanced (N=xxxx)	Metastatic (N=xxxx)	Total (N=xxxx)
Number of patients screened	xxxx	xx	xxxx
Screening failure	x	x	x
Safety Evaluable Population	xxxx	xx	xxxx
Total Exclusions	xx	x	xx
Intent to Treat Population	xxxx	xx	xxxx
Total Exclusions	xx	x	xx
mBCC Protocol 4(+) Patients (1)	x	xx	xx
8-Weekly Tumour Assessment (2)	xxx	xx	xxx
First Consented Protocol Version: 1	xxx	xx	xxx
First Consented Protocol Version: 2	xxx	xx	xxx
First Consented Protocol Version: 3	xxx	xx	xxx
First Consented Protocol Version: 4	xx	x	xx
First Consented Protocol Version: 5	x	xx	xx
Last Consented Protocol Version: 1	xx	x	xx
Last Consented Protocol Version: 2	xxx	xx	xxx
Last Consented Protocol Version: 3	xxx	xx	xxx
Last Consented Protocol Version: 4	xxx	xx	xxx
Last Consented Protocol Version: 5	xxx	xx	xxx
Last Consented Protocol Version: 6	xx	x	xx

#### Programming Note:

- N is Number of Patients present in each of Disease status category i.e. Locally Advanced or Metastatic.
- Number of Patients screened and screen failure information comes from the CRF.
- Number of Subjects Excluded from Safety/Intent to Treat population are the Patients excluded from Safety/Intent to Treat population other than screen failures.
- See Patient Population section for information about populations.
- Patient's First and Last protocol consent information comes from the CRF.

## Listing of Patients Populations

Disease Status: Locally Advanced									
Center/ Patient ID	All Subjects	Screening Failure	Safety Population	ITT Population	mBCC Protocol Patients	4(+) 8- Weekly Tumour Assessment	First Consented Protocol Version	Last Consented Protocol Version	
xxxxxx/xxx	Yes	No	Yes	Yes	No	No	x	x	
xxxxxx/xxx	Yes	No	Yes	Yes	No	No	x	x	
xxxxxx/xxx	Yes	No	Yes	Yes	No	No	x	x	
xxxxxx/xxx	Yes	No	Yes	Yes	No	No	x	x	

### Programming Note:

- Listing will display whether the Patients are included or excluded from the Population.
- See Patient Population section for information about populations.
- Patient First/last consented to protocol version information comes from CRF page.
- All Patients with non-missing disease status are included in the listing.

### Programming Note:

- Only include patients who are excluded from Safety Population and are not screen failures.

## Disposition:

Patients will be considered to have completed the study if they have discontinued or completed treatment, and have completed their follow-up period (1 month for subjects who enrolled to protocol version 1 or 2, or 12 months for subjects who were enrolled to protocol 3 or later).

The reason for discontinuation of the study comes from the End of Follow Up CRF Page and should be listed under reasons for Study Discontinuation based on Safety and Non-safety categories.

Patients discontinued from treatment for a variety of reasons (recorded in the End of Study Treatment CRF page), and these should be listed under reasons for treatment discontinuation based on Safety and Non-safety categories.

Note: under the treatment discontinuation category, those who recorded “withdrew from treatment” in the CRF were assumed to have also left the study (as the investigators were additionally asked for study withdrawal information). As a result, patients who discontinued treatment but remained in follow-up were counted in the “Other” category. A footnote to the discontinuation table should be added to explain this idiosyncrasy.

## 1. Patient Disposition

DST01	
Output ID: t_ds_*
 

● Analysis Population: Safety-Evaluable Patients

● Column Variables: Disease status (Locally Advanced, Metastatic)

● Column Totals: Total of non-missing Disease status

● Analysis Variables:

Number of Patients Completed study

○ Follow-up of 1 month

○ Follow-up of 12 months,

Number of Patients discontinued from Study ,

○ Safety

○ Non-Safety

Number of Patients Ongoing in Study

○ In Follow-Up

○ On Treatment,

Number of Patients discontinued from Treatment

○ Safety

○ Non-Safety

● Numeric Precision and Formatting of Statistics: Use standard display in the mockup

--------------	--

### Programming Note:

1. Patients are considered as completers (i.e. included in the row *Number of Patients Completed Study*) if an End of Follow-Up (EOFU) page is present, or (for patients whose EOFU page was missing due to a known database issue where the EOFU page was not available), one of the following conditions is met:
  - a. for subjects whose latest protocol version consented to was 1 or 2, they were alive at the date of their 30 day FU visit.
  - b. for subjects whose latest protocol version consented to was 3 or higher, they were alive at the date of their 12 month FU visit.
2. Patients who completed (as per point 1) were sub-categorised as having completed “Follow-up of 1 month” if their latest protocol consented to was version 1 or 2, or having completed “Follow-up of 12 months” if their latest protocol consented to was version 3 or a subsequent version.
3. For the sub-categories of *Number of patients discontinued from treatment*: reasons of “Adverse Event” and “Death” are classified as *Safety*; any other reasons are classified as *Non-Safety*.
4. For the sub-categories of *Number of patients ongoing in study*: patients categorised as *in Follow up* include the patients who have discontinued from treatment (but are still in the study); patients categorised as *On Treatment* include patients still receiving treatment.
5. If the reason for Study Discontinuation is the same as the reason for Treatment Discontinuation then the record should be included in both sections of the display.

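### The disposition notes count any patient with an End of Follow-Up page as having completed the study, although the SAP defines completion by follow-up and reads study-discontinuation reasons from that same page (minor)

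*SAP*

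**What the plan says.** The opening text of the SAP's Disposition section requires two things of a completer: treatment has ended, and patients "have completed their follow-up period". That period is 1 month for protocol versions 1 and 2, and "12 months for subjects who were enrolled to protocol 3 or later". The section then adds: "The reason for discontinuation of the study comes from the End of Follow Up CRF Page".

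Under 1. Patient Disposition (output t_ds_*), Programming Note 1 gives the rule for the completed row. A patient is included "if an End of Follow-Up (EOFU) page is present". Only where the page is missing because of a known database problem is there a further test, namely survival to the follow-up visit. For version 3 or higher this reads "they were alive at the date of their 12 month FU visit"; for versions 1 and 2 the 30-day visit is used.

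Note 2 splits completers by length of follow-up using consent version only. They go into the 12-month group "if their latest protocol consented to was version 3 or a subsequent version".

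The table also has a separate row, "Number of Patients discontinued from Study". Note 2 of the 24-week table repeats the page-present rule, and the 52-week table is specified as a repeat of the 24-week one.

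**The concern.** A page that collects reasons for leaving the study is not evidence that follow-up was finished. If its mere presence makes someone a completer, the completed row mixes patients who were followed to the end with patients who left early. Its 12-month sub-row then no longer shows how many patients were observed for 12 months off drug, which is what a reader of a safety study would take from it.

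In the main table the same patient could stand in both the completed and the discontinued-from-study rows. The 24- and 52-week tables list only completed and discontinued-from-treatment rows, so nothing in them would reveal the problem.

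**Working it through.** The plan states no figure to reproduce, so the check is mainly a comparison of texts, followed by a sensitivity per patient.

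**Step 1: what the page can contain.** The Disposition section makes it the source of study-discontinuation reasons. The Deaths section under General Considerations lists it among the sources of date of death (the Death page prevails if dates differ). It can therefore exist for patients who did not finish follow-up.

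**Step 2: one patient under each rule.** Take a hypothetical patient whose latest consent is to version 3, who stops treatment and withdraws between the 3- and 6-month follow-up visits.

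| Rule | Result |
|---|---|
| Definition in Disposition text | Not completed: the 12-month period was not finished |
| Note 1, page present | Completed |
| Note 2 | Placed in the 12-month follow-up sub-row |
| Study-discontinuation row, reason read from the page | Also counted there |
| Note 1, page missing for the known database reason | Not completed: no 12-month visit at which to be alive |

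The last line shows the asymmetry: patients without the page face a test that patients with it do not. Compared with the definition, the page-present branch can only add completers.

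**Step 3: does another note repair it?** Note 5 deals with overlap, but only where the reason for leaving the study equals the reason for stopping treatment: "then the record should be included in both sections of the display". No note makes completed and discontinued from study exclusive. The SAP does use a better rule elsewhere: the PV3COMP population identifies 12-month completers from the 12-month follow-up record.

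**Step 4: version basis.** The Disposition text sets the follow-up length by the version enrolled to; Notes 1 and 2 use the latest version consented to. The Patient Populations shell tabulates first and last consented versions separately, and has a row for version 6 as last but not as first, so the two are expected to differ. A patient enrolled under version 2 who later consented to version 3 owes 1 month under the text and 12 months under the notes. PV3COMP and the Potentially Reversible AE population both go by consent to version 3 or higher at any point, which agrees with the notes as long as re-consent only moves to later versions.

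**Step 5: size.** Denominators are the safety-evaluable counts in the SAP's Summary of Deaths: 1119 locally advanced, 96 metastatic, 1215 in total. Shift in the completed percentage of the main table per miscounted patient = 1/N:

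- total: 1/1215 = 0.08 points
- locally advanced: 1/1119 = 0.09 points
- metastatic: 1/96 = 1.04 points

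The denominators of the 24- and 52-week tables are not given.

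**The case against.** The strongest reply is that the intent is plain. The governing definition opens the section, completed, discontinued and ongoing are laid out as separate rows, and the fallback tests show that the page was meant to stand for reaching the end of follow-up. The page's fields are not shown, and the program may already filter on a recorded completion status. This stands as far as consequence goes: nobody may be miscounted. It does not rescue the wording, because the note is the operative rule for the row and a programmer following it would code something other than the definition. The SAP points to its DAP M3 specification for other derivations, such as visit windowing and the data cut, but these notes do not.

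A second reply is that nothing important depends on the row. This also largely stands. Completion is not among the variables in Protocol 8.1.1 or 8.1.2. The primary safety variable is premature discontinuation from study and treatment, which the discontinued rows still report. No hypothesis is tested. PV3COMP does not use page presence.

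A reader might infer from the 110 deaths among 1215 patients (9.1%) in the Summary of Deaths that completion is overstated by up to that amount. The documents do not support this. They do not say when those deaths fell relative to the end of follow-up or whether those patients have the page. Nor is it an upper bound, since withdrawals and losses to follow-up would count too.

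**Conclusion.** The counting rule is wrong as written: it does not implement the SAP's own definition, and followed literally it counts early leavers who have the page as completers. The point is minor. It reaches only the completed rows of three descriptive disposition tables. The number affected cannot be determined from the documents and may be zero; the metastatic column is the most sensitive, at 1.04 points per patient. The conclusion assumes that the notes are coded as they read and that at least some early leavers have the page. The documents do not support the stronger inference that the safety conclusions, the study-discontinuation counts or the 12-month completer population are distorted.

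**What to change.** - In Note 1 of the main table and Note 2 of the 24-week table, count a patient with an End of Follow-Up page as completed only if the page, or the follow-up visit record as in PV3COMP, shows that the applicable follow-up period was completed. Keep the existing test for missing pages. The 52-week table inherits the change.
- Count patients whose page records early study discontinuation, or death before the end of follow-up, only as discontinued from study. Word the rule by what the page shows, not by the absence of a discontinuation reason: if completion is coded in the same field, an absence rule would drop true completers.
- Check at patient level that nobody is in more than one of completed, discontinued from study and ongoing. Confirming that the three rows do not exceed N is not enough, since patients who fall in no row can mask an overlap.
- In the Disposition text, replace the enrolled-version basis with latest version consented to. Keeping the enrolled version would conflict with PV3COMP and the Potentially Reversible AE population.

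The cost is one clause in two notes, one wording change, the patient-level check and a rerun of three tables. If the program already filters on completion, only the wording changes. The downside is that the reported completion count may fall.

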## 2. Patient Disposition within 24 weeks of first dose

DST01	Output ID: t_ds_24wkdisc_* 

● Analysis Population: Safety-Evaluable Patients

● Column Variables: Disease status (Locally Advanced, Metastatic)

● Column Totals: Total of non-missing Disease status

● Analysis Variables:

Number of Patients Completed study

Number of Patients discontinued from Treatment

○ Safety

○ Non-Safety

● Numeric Precision and Formatting of Statistics: Use standard display in the mockup

--------------	--

### Programming Note:

1. Only include Patients whose overall Duration of study treatment is less than or equal to 24 weeks i.e. less than equal to 168 days from first valid dose.
2. Patients are considered as completers (i.e. included in the row *Number of Patients Completed Study*) if an End of Follow-Up (EOFU) page is present, or (for patients whose EOFU page was missing due to issues with the system), one of the following conditions is met:
  - a. for subjects whose latest protocol version consented to was 1 or 2, they were alive at the date of their 30 day FU visit.
  - b. for subjects whose latest protocol version consented to was 3 or higher, they were alive at the date of their 12 month FU visit.
3. For the sub-categories of *Number of patients discontinued from treatment*: reasons of "Adverse Event" and "Death" are classified as *Safety*; any other reasons are classified as *Non-Safety*.

### 3. Patient Disposition within 52 weeks of first dose

Output ID: t\_ds\_52wkdisc\_\*

Repeat t\_ds\_24wkdisc\_\* output for Patients whose overall Duration of study treatment is less than equal to 52 weeks i.e. less than equal to 364 days from first valid dose.

### 4. Listing of Primary Reason for Patients Prematurely Discontinuing Treatment

Disease Status: Locally Advanced

Center/ Patient ID	Age/Sex/Race	Date of First Study Drug Administration	Day of Last Study Drug Administration	Day of Treatment Discontinuation	Reason for Treatment Discontinuation	Other Reason for Treatment Discontinuation
xxxxxx/xxx	x	xxxx-xx-xx	xxx	xxx	ADVERSE EVENT	
xxxxxx/xxx	x	xxxx-xx-xx	xx	xx	ADVERSE EVENT	
xxxxxx/xxx	x	xxxx-xx-xx	xxx	xxx	PROGRESSIVE DISEASE	
xxxxxx/xxx	x	xxxx-xx-xx	xx	xx	ADVERSE EVENT	
xxxxxx/xxx	x	xxxx-xx-xx	xx	xx	ADVERSE EVENT	
xxxxxx/xxx	x	xxxx-xx-xx	xxx	xxx	ADVERSE EVENT	
xxxxxx/xxx	x	xxxx-xx-xx	xxx	xxx	PROGRESSIVE DISEASE	
xxxxxx/xxx	x	xxxx-xx-xx	xxxx	xxxx	WITHDRAWAL BY SUBJECT	
xxxxxx/xxx	x	xxxx-xx-xx	xxx	xxx	ADVERSE EVENT	
xxxxxx/xxx	x	xxxx-xx-xx	xxx	xxx	OTHER	'Patient requested to discontinue treatment but agreed to continue in follow up'

Programming note:

- Include safety evaluable patients who discontinued from study drug treatment.
- Variables to include: Centre, Subject, Age, Sex, Race, Date of Treatment Start, Day of Last Treatment, Study Day of Treatment Discontinuation, Reason and Other Reason for Treatment Discontinuation.
- Please see programming notes for the l\_ds\* output.
- Please see information for the output ID: DSL02.

## Demographic:

### 1. Demographic and Baseline Characteristics

DMT01	
Output ID: t_dm_*
 

● Analysis Population: Intent-to-Treat Patients

● Column Variables: Disease status (Locally Advanced, Metastatic)

● Column Totals: Total of non-missing Disease status

● Analysis Variables: Age (Years), Age group (years), Sex, Race, Height (cm) at baseline, Weight (kg) at baseline, BMI (kg/m^2), Temperature (C), Years from First BCC Diagnosis to Dose, Baseline ECOG Performance Status, Gorlin Syndrome, Child Bearing Potential (Females), Number of Target Lesions at Baseline.

● Statistics and Calculation Methods: Use Proc means for Summary Statistics and Proc freq for Frequency Counts. Summary Statistics should be displayed for following analysis variables. Age(Years), Height (cm) at baseline, Weight (kg) at baseline, Years from First BCC Diagnosis to Dose, Number of Target Lesions at Baseline Frequency counts should be displayed for following analysis variables: Age group (years), Sex, Race, Baseline ECOG Performance Status, Gorlin Syndrome, Child Bearing Potential (Females)

● Numeric Precision and Formatting of Statistics: Use standard display in the mockup

--------------	--

#### Programming Note:

1. N is Number of Patients present in each *Disease Status* category i.e. Locally Advanced or Metastatic.
2. The variable *Baseline Age (varname BAGE)* should be used for Age information (in Age (years) and Age group (years) section). Baseline Age is the Patient's age (years)

at the informed consent (to study) date and it is derived from Informed consent date and Imputed Birth date (ASL.BAGE):  
(Set to integer part of (Informed consent date – Imputed Birth Date +1)/365.25).

If Birth date of subject is partial (at least year of Birth date is present) then use the following Missing Data Handling Rule:

- If the day part of the birth date is missing, impute it with 15.
  - If the month part of the birth date is missing, impute it with June.
- Age categories should be derived on the basis of Baseline Age.

3. Sex, Height, Weight, and Temperature information come from the Demography and Vital Signs CRF page. BMI is derived using the common formula defined in the DAP M3.

4. Race information comes from the Demography CRF page and as per SDTM controlled terminology

“Black” should be mapped as “Black or African American”.

Race was recorded as “Not applicable” in France.

5. Years from First BCC Diagnosis to Dose should derived as difference between First Treatment start Date and Date of First BCC Diagnosis comes from CRF page divided by year i.e. 365.25 days.

If First BCC Diagnosis date is partial then

a) Impute to the first day of the month if the day is missing.

b) Impute to the first month of the year if the month is missing.

6. Baseline ECOG Performance Status, Gorlin Syndrome, Child Bearing Potential information comes from CRF.

7. Number of Target Lesion at Baseline should be calculated as total number of target Lesions collected on last Tumor assessment date which is on or prior to First Dosing date having non missing Tumor Location and Tumor assessment date.

